**5. Inclusion/Exclusion Criteria**

The inclusion and exclusion criteria for participants in this trial are listed in the table below.

Eligibility criterion	Rationale
Diagnosis of Progressive MS based on Lublin criteria	We are focusing on people with PMS since they are more likely to have low bile acid levels
Age ≥ 18 years	To include only adults in the trial
On the same therapy for the past 6 months and not expected to switch therapy in the next 6 months	To avoid confounding by changes in immunomodulatory therapy during the trial
No relapse in the past 3 months	To avoid any confounding introduced by relapse
Exclusion criterion	Rationale
No previous history of liver disease	Confounding due to decreased bile acid production or altered bile acid metabolism
No stage IV/V chronic kidney disease or other severe metabolic derangements	To reduce risk of adverse effects or confounding due to other systemic disorders
BMI < 15 kg/m  and BMI > 40 kg/m 	Reduce confounding due to extremes of BMI
Female patients who are pregnant or nursing, or not	Prevent potential teratogenicity

willing to use contraception	
Chronic antibiotic use	Prevent confounding of microbiome analyses
Corticosteroid treatment within the past 30 days	Prevent confounding of treatment effect
Known history of other neuroinflammatory, neurodegenerative or systemic autoimmune disease	These diseases could require other treatments or be affected by the trial medication.
No current or prior history of the following – 
 
• Bariatric surgery
 
• Small intestinal surgery resulting in loss of length of the jejunum or ileum
 
• Chronic diseases of the small intestine (e.g., Crohn’s Disease, gluten sensitive enteropathy, or other disorders that could lead to malabsorption)
 
• Abnormal bile duct anatomy
 
• Sclerosing cholangitis
 
• Anti-mitochondrial antibodies
 
	These conditions could alter bile acid handling in the gut or bile acid levels in circulation

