**6. Drugs/ Substances/ Devices**

**a. The rationale for choosing the drug and dose or for choosing the device to be used.**

Tauroursodeoxycholic acid (TUDCA) is a hydrophilic bile acid that is normally produced endogenously in humans in the liver, by conjugation of taurine to UDCA. It is used in Europe to treat cholestatic liver disease and gallstones. TUDCA has been used in trials for liver cirrhosis, primary biliary cirrhosis, transthyretin related amyloidosis, cholesterol gallstones, diabetes, and ALS[30]–[33], with a good safety profile. Diarrhea was the most common side effect noted in these studies, which utilized varied doses of TUDCA.

As noted in the background section, we chose TUDCA as an intervention since it has been previously demonstrated to be safe and have several beneficial effects (on ER stress, mitochondrial dysfunction, immunological effects and neuroprotection) that could potentially lead to benefits in patients with MS. Additionally since TUDCA can change the circulating bile acid pool this could potentially help correct this metabolic abnormality that we have identified in our preliminary studies.

We will obtain TUDCA from Bruschetini S.r.l (Genoa, Italy). This medication is manufactured as 250 mg capsules and hence participants will take 4 capsules two times a day of either TUDCA or placebo. The study medication will be provided through the Johns Hopkins investigational drug services and will appear identical to maintain blinding. TUDCA is approved in Italy for the treatment of cholestasis and gallstones. It was recently accorded orphan drug status by the European Medicines Agency for the treatment of Amyotrophic lateral sclerosis.

Dose: We chose a dose of 1 gm BID based on the trial of TUDCA in ALS that was recently completed across three centers in Italy[25]. Participants in this trial had no significant adverse

events on TUDCA, and there appeared to be some evidence for a benefit in this early phase study. This dose is higher than the dose utilized in treatment of cholestatic disease and is close to the 30 mg/kg dose utilized in a trial of UDCA in ALS that was well tolerated and showed no significant difference in serum and CSF concentrations compared to a higher dose of 50 mg/kg[27],[30].

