**b. Secondary outcome variables.**

1. Metabolomics – We will store plasma before and after the study intervention to assess the effect of the study medication on fasting bile acid levels. This will enable us to determine whether the study drug raised the levels of bile acids that were deficient in people with MS. Targeted metabolomics analyses will be performed through Metabolon Inc.
2. Gut microbiota – The composition of the gut microbiota is closely related to bile acid metabolism, and alterations in bile acid receptor (FXR) signaling can significantly affect composition of the gut microbiota[37],[38]. We will collect first morning stool specimens prior to and following study treatment to determine the effect of bile acid supplementation on the gut microbiota in people with MS.
3. Immunophenotyping – We will store PBMCs from before and after the study intervention to assess the effect of TUDCA supplementation on the peripheral immune system. Our laboratory has expertise in immunophenotyping people with MS and assessing the effect of

therapeutic interventions on peripheral immune cell function. These assays will be performed at the end of the study.

4. Other outcomes – We will also collect information regarding quality of life using the MSQOL-54 instrument[39] administered at the visits noted in the table above. We will also measure lipid profile and hemoglobin A1c at baseline and end-of-study, since bile acid metabolism is linked to obesity and metabolic syndrome.

Assessment of important covariates: We will collect demographic information including age, gender, cigarette smoking, waist circumference, and BMI which can affect circulating bile acid levels. Another critical factor that can affect bile acid metabolism and the gut microbiota is diet. Since TUDCA could potentially lead to GI side effects, this may result in a change in diet. To monitor changes in diet we will perform the Block Food frequency questionnaire before and after the study intervention. Since antibiotics and probiotics can lead to changes in the gut microbiome and could also affect bile acid metabolism, we will collect detailed information on the use of both these covariates so they can be adjusted for in our final analyses.

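### Entry criteria screen out diseases that alter bile acids but not use of bile acid products or binders, and exclude only chronic antibiotic use, so baseline research samples can already be disturbed

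*Combined protocol and SAP*

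**What the plan says.** Section 5 excludes bariatric and small-bowel surgery, chronic small-intestinal disease, abnormal bile duct anatomy, sclerosing cholangitis and anti-mitochondrial antibodies. The reason given is "These conditions could alter bile acid handling in the gut or bile acid levels in circulation". Previous liver disease is a separate exclusion. No drug or supplement appears in this group.

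Two other exclusions concern medication. One is "Chronic antibiotic use", with the rationale "Prevent confounding of microbiome analyses"; chronic is not defined and no period before baseline is given. The other is "Corticosteroid treatment within the past 30 days", which does have a period. A separate entry criterion requires stable treatment ("On the same therapy for the past 6 months and not expected to switch therapy in the next 6 months"), with the rationale "To avoid confounding by changes in immunomodulatory therapy during the trial".

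Section 6a says of TUDCA: "It is used in Europe to treat cholestatic liver disease and gallstones". Its pharmacokinetics paragraph gives a 1.9 to 8 fold change in total serum bile acids when UDCA or TUDCA is taken.

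Concomitant medication is reviewed at every visit, and the schedule in Section 4a names antibiotics and probiotics. Section 7b gives the reason: "Since antibiotics and probiotics can lead to changes in the gut microbiome and could also affect bile acid metabolism". It intends to adjust for those two. In Section 7c the metabolomics models name BMI, age, gender and diet measures as covariates; the list is introduced as non-exhaustive.

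**The concern.** The entry criteria guard against indirect causes of altered bile acids but leave open the most direct one, which is taking a bile acid. They also guard the microbiome against long-term antibiotics but not against a course that ended days before the first stool sample.

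Aims 1 and 2 rest on changes from before to after treatment. Someone already taking a bile acid at baseline may have less room to change on TUDCA. A placebo participant who starts one may look like a treated participant. A stool sample taken soon after antibiotics makes ordinary recovery of the flora look like a change during treatment. Section 4e says that the placebo arm is there to show whether bile acid, microbiota and immune changes are due to TUDCA, and Section 7c sizes the trial on bile acid change. These are therefore the comparisons exposed.

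**Working it through.** **1. Who can enter, and with what sample**

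| Exposure | Entry criterion (Section 5) | Recorded | Named for adjustment (Sections 7b, 7c) |
|---|---|---|---|
| Bile acid product | None. Liver disease, sclerosing cholangitis and anti-mitochondrial antibody exclusions remove some users | Only under general medication review | No |
| Bile acid binder | None | Only under general medication review | No |
| Short antibiotic course before baseline | None; chronic use only | Yes, by name | Intended in 7b, not listed in 7c |
| Newly started probiotic | None | Yes, by name | Intended in 7b, not listed in 7c |

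The stable-therapy criterion does not close the gap. Its rationale concerns immunomodulatory treatment, and a long-term bile acid user would satisfy it anyway. Gallstones, a use of TUDCA named in Section 6a, are not an exclusion.

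Under the three-visit option in Section 4a, research blood and stool are taken at screening. For those participants the baseline samples are collected at the same visit as the first medication review.

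**2. What the analysis can repair**

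A covariate in a mixed model can absorb part of the disturbance if it is named. The paired t tests that Section 7c plans for immune cell subsets compare a person with him- or herself and carry no covariate. Section 3 states that metabolites made by gut microbes, bile acids among them, act on immune cells, so a disturbed baseline can reach these outcomes too.

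**3. The plan's own sample size**

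Inputs from Section 7c: 50 to 70% change, power 85%, two-sided alpha 0.05, 14 to 27 per arm, 10% drop-out.

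- Recruitment: 27 / (1 − 0.10) = 30 per arm, as stated.
- The SD is not given. Solving SD = change / [(1.960 + 1.036) × √(2/n)] gives 0.50 / (2.996 × 0.272) = 0.613 at n = 27, and 0.70 / (2.996 × 0.378) = 0.618 at n = 14. A single SD of about 0.61 reproduces both ends, so the range is consistent.

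**4. Size of the dilution (illustration)**

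The share of users is not in the documents. Suppose a share f of each arm shows no TUDCA-placebo contrast. The effect is then multiplied by (1 − f).

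- With 2 of 27 per arm, f = 2/27 = 7.4%. On the log scale a 1.9 fold effect goes from 0.642 to 0.642 × 25/27 = 0.594, and an 8 fold effect from 2.079 to 1.925. The proportion lost is the same whatever the fold.
- Two placebo participants of 27 who start the same product during the study lose the same 7.4% of the contrast.
- Power at 27 per arm for the 50% target with SD 0.613:

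| Share f | Effect 50% × (1 − f) | Power | Evaluable per arm for 85% |
|---|---|---|---|
| 0% | 50.0% | 85.0% | 27 |
| 5% | 47.5% | 81.2% | 30 |
| 10% | 45.0% | 76.9% | 34 |
| 20% | 40.0% | 66.9% | 43 |

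The documents give no effect size for binders or for antibiotics on these outcomes, so neither is quantified here.

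**The case against.** Nothing in the documents shows that any entrant takes or would start these products, and with no users the effect is nil. The liver-related exclusions already remove one of the two European uses of TUDCA named in Section 6a. For the other, gallstones, the documents mention use in Europe and approval in Italy, and Section 6c describes the drug as not FDA approved. Antibiotic and probiotic use is recorded and meant to be adjusted for. All of this stands, and it keeps the point modest.

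Three stronger readings are tempting, and the documents do not support them.

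- *Systematic bias between the arms.* Prior bile acid use and recovery after antibiotics are balanced by randomization in expectation. Flora recovery misread as a treatment effect is mainly a risk for within-arm comparisons. Between arms it adds noise and possible chance imbalance.
- *A loss of 12 to 38% of the target effect.* This comes from giving 2 of 27 placebo participants a 1.9 to 8 fold rise (2/27 × 0.642 = 0.048; 2/27 × 2.079 = 0.154) and dividing by ln 1.5 = 0.405. It sets a change in total bile acids against a target for an individual bile acid, and lets the product act more strongly in the placebo arm than TUDCA does in its own arm. The consistent figure is 7.4%.
- *A collapse in power.* If 5 to 20% of entrants arrive with levels raised 8 fold and levels are compared without using baseline, the log SD rises from 0.497 to between 0.673 and 0.969, and power falls to between 60% and 34%. Section 7c also plans a longitudinal mixed model across visits, so this is not a fair picture of the planned analysis.

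What survives is that the plan states a purpose for these exclusions and the wording does not meet it.

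**Conclusion.** The gap is real and limited. The entry criteria allow current or recent use of bile acid products and binders, and short antibiotic courses just before the baseline stool. Bile acid products and binders are also missing from the adjustment plan. The consequence is dilution, added variance, chance imbalance with 30 per arm, and distorted within-arm changes in the secondary metabolomic, microbiome and immune outcomes.

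The illustrative size is about 7% of the effect if 2 of 27 per arm show no contrast. It rests on an assumed number of users, on users showing no further change, and, for the power figures, on an SD solved back from the stated sample size. A reader might infer that the primary result is in doubt; the primary outcome is adverse events and drop-out (Section 7a), and no effect on it is shown here. The correction is worth making because it is cheap and matches the protocol's own reasons for these criteria.

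**What to change.** **Section 5.** Add current or recent use of a bile acid product or bile acid binder to the exclusions. Define chronic antibiotic use, and add a look-back period for any systemic antibiotic and any newly started probiotic before the baseline research samples. The investigators should set and justify the lengths. The 30 days used for corticosteroids is not supported in the documents as a period for bile acids or the microbiome.

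**Section 4a.** Under the three-visit option, check these exposures before the screening visit, because the research blood and stool are taken there and postponing the baseline visit would not protect them.

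**During the study.** Record use of bile acid products and binders by name at the existing medication reviews, next to antibiotics and probiotics. No rule on concomitant treatment is proposed.

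**Section 7c.** Name these exposures as covariates in the metabolomic, microbiome and immune models. Add a sensitivity analysis that leaves out exposed participants or samples, and repeat the paired tests on that set.

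**Cost.** A few participants are excluded or wait before baseline sampling, and a short medication check is needed before the first sampling visit. The stated sample size does not change.

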**6. Drugs/ Substances/ Devices**

**a. The rationale for choosing the drug and dose or for choosing the device to be used.**

Tauroursodeoxycholic acid (TUDCA) is a hydrophilic bile acid that is normally produced endogenously in humans in the liver, by conjugation of taurine to UDCA. It is used in Europe to treat cholestatic liver disease and gallstones. TUDCA has been used in trials for liver cirrhosis, primary biliary cirrhosis, transthyretin related amyloidosis, cholesterol gallstones, diabetes, and ALS[30]–[33], with a good safety profile. Diarrhea was the most common side effect noted in these studies, which utilized varied doses of TUDCA.

As noted in the background section, we chose TUDCA as an intervention since it has been previously demonstrated to be safe and have several beneficial effects (on ER stress, mitochondrial dysfunction, immunological effects and neuroprotection) that could potentially lead to benefits in patients with MS. Additionally since TUDCA can change the circulating bile acid pool this could potentially help correct this metabolic abnormality that we have identified in our preliminary studies.

We will obtain TUDCA from Bruschetini S.r.l (Genoa, Italy). This medication is manufactured as 250 mg capsules and hence participants will take 4 capsules two times a day of either TUDCA or placebo. The study medication will be provided through the Johns Hopkins investigational drug services and will appear identical to maintain blinding. TUDCA is approved in Italy for the treatment of cholestasis and gallstones. It was recently accorded orphan drug status by the European Medicines Agency for the treatment of Amyotrophic lateral sclerosis.

Dose: We chose a dose of 1 gm BID based on the trial of TUDCA in ALS that was recently completed across three centers in Italy[25]. Participants in this trial had no significant adverse

events on TUDCA, and there appeared to be some evidence for a benefit in this early phase study. This dose is higher than the dose utilized in treatment of cholestatic disease and is close to the 30 mg/kg dose utilized in a trial of UDCA in ALS that was well tolerated and showed no significant difference in serum and CSF concentrations compared to a higher dose of 50 mg/kg[27],[30].

Pharmacokinetics of TUDCA: Previous studies have demonstrated that about 65% of the oral dose of TUDCA is absorbed and then undergoes first pass metabolism in the liver followed by extensive enterohepatic circulation[34]. Administration of bile acids such as UDCA and TUDCA results in a change in the overall serum bile acid concentration – between 1.9 – 8 fold and alters the composition of the bile acid pool[35],[36]. A trial of UDCA in ALS also demonstrated dose-dependent increased in CSF concentrations of the bile acid[27].

**b. Justification and safety information if FDA approved drugs will be administered for non-FDA approved indications or if doses or routes of administration or participant populations are changed.**

N/A

**c. Justification and safety information if non-FDA approved drugs without an IND will be administered.**

We are using a non-FDA approved drug, however this will be utilized either with an IND or with an IND waiver from the FDA.

## 7. Study Statistics

**a. Primary outcome variable.**

The primary outcome of this study is the safety and tolerability of TUDCA supplementation. This will be based on number of adverse events occurring in the two treatment groups and the rate of drop-out in each study arm. This data will be documented at each study visit.

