**f. Definition of treatment failure or participant removal criteria.**

Patients selected for the study will be removed if they:

- 1) They develop abnormal safety labs as defined below
- 2) Develop a serious adverse event
- 3) Inform us that they became pregnant during the study
- 4) Are unable to follow the requirement of the study
- 5) Request to be removed

**g. Description of what happens to participants receiving therapy when study ends or if a participant's participation in the study ends prematurely.**

The subject's medical care will continue unaltered when the study ends or if a subject is removed from the study.

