**c. Statistical plan including sample size justification and interim data analysis.**

Safety data will be analyzed as they are captured in real time. Assessments will focus on AEs (including study treatment tolerability assessments, laboratory evaluations, vital signs and physical examination). The incidence rate of AEs will be recorded by system organ class, severity and by relationship to study treatment. Tolerability analysis will be based on the number (%) of participants who failed to complete the study due to adverse events. Lab values for each parameter will be summarized by shift tables. For quantitative parameters, we will present summary statistics for actual values and change from baseline. We will compare changes over the 16-week treatment period between the groups using mixed effects regression analyses to account for repeated measures using random subject-specific intercepts and slopes.

Metabolomics data will be analyzed at the end of the study following quantitation of the 15 bile acids included in our panel. Summary statistics will be used to characterize these outcomes. We will then assess normality of these measures and perform appropriate univariate testing to determine which bile acids are significantly altered by TUDCA supplementation. A mixed effects longitudinal model will also be used to test which bile acids are altered between visits across the two groups. Models will also adjust for important covariates including BMI, age, gender and measures derived from the food frequency questionnaire.

Gut microbiota data, *a priori* analyses will assess changes in relative abundances of different gut bacteria as well as microbial genes that encode bile acid metabolizing enzymes (identified from the literature and NCBI Gene database) which occur as a result of TUDCA treatment. Exploratory analysis will assess the effects of TUDCA on the metagenome using a combination of pathway and set-based approaches previously applied in metagenomics analysis of MS and other diseases to identify other biologically relevant changes[41]–[43].

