#### **d. Early stopping rules.**

We will discontinue treatment if a participant develops abnormal safety labs (serum AST or ALT > 3 x upper limit of normal, serum bilirubin > 3 x upper limit of normal, eGFR < 60ml/min/1.73m^2), becomes pregnant during the study, cannot tolerate the drug, develops an adverse event grade 3 or higher that is possibly related to study treatment or wants to discontinue treatment. Any death that is at least possibly related to the study will put the study on hold. The Data and Safety Monitoring Board will determine if it is safe to resume the study. Subjects who become suicidal during the study (codes 1-4, <http://www.fda.gov/downloads/Drugs/GuidanceComplianceRegulatoryInformation/Guidance/UCM225130.pdf>) will be referred to a psychiatrist or to a psychiatric emergency room for evaluation at the discretion of the site treating physician.

Data and Safety Monitoring Board (DSMB): An independent DSMB will be utilized for subject monitoring. The DSMB will consist of a neurologist, a hepatologist and a statistician. The DSMB will meet every 12 weeks and any time an SAE occurs. All SAEs will be reported to the DSMB delegates within 24 hours of the study staff becoming aware of the SAE. The DSMB will be required to review SAEs and respond with recommendations within two business days. If more than 3 subjects experience serious adverse events, the study will be put on hold and the DSMB will decide on whether the adverse events were secondary to study treatment. They will make a judgement as to whether the study should continue and, if so, whether a reduction in TUDCA dosing or other protocol modifications are recommended.

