### c. Plan for reporting unanticipated problems or study deviations.

Unexpected Adverse Event: An adverse event is considered unexpected when its nature or severity is not consistent with the product information (e.g. package insert safety information, the investigational plan, the investigator's brochure, the protocol, or the informed consent form).

Serious Adverse Event: A serious adverse event (any adverse event that suggests a significant hazard, contraindication, side effect, or precaution) must be reported. This includes, but may not be limited to, death, a life-threatening event, inpatient hospitalization or prolongation of existing hospitalization, persistent or significant disability/ incapacity, congenital anomaly/ birth defect, other protocol-specified conditions, or an event that requires intervention to prevent permanent impairment or damage. Serious adverse events will be collected from informed consent signing until 30 days after study completion or until 30 days after a participant withdraws from the study.

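### The adverse-event half of the primary outcome is a raw count per arm, with no exposure denominator and no stated collection of non-serious events after removal, so unequal early exit biases the comparison

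*Combined protocol and SAP*

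**What the plan says.** Section 7a gives the primary outcome two components: "This will be based on number of adverse events occurring in the two treatment groups and the rate of drop-out in each study arm". It adds that these data are documented at the study visits. After baseline those are weeks 8 and 16; Section 4b adds unscheduled visits for adverse events or new symptoms. No early-termination visit is listed.

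Section 7c describes the analysis in different terms: "The incidence rate of AEs will be recorded by system organ class, severity and by relationship to study treatment". It does not say whether the denominator of that rate is participants or person-time. For tolerability it says: "Tolerability analysis will be based on the number (%) of participants who failed to complete the study due to adverse events". That is narrower than the drop-out rate of Section 7a, which is not limited to any cause.

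Two sections govern early exit:

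- Section 4f opens with "Patients selected for the study will be removed if they" and lists abnormal safety labs, "Develop a serious adverse event", pregnancy, inability to meet study requirements, and the participant's request. The consequence is leaving the study.
- Section 7d says "We will discontinue treatment if a participant develops abnormal safety labs", and extends this to pregnancy, intolerance, and a participant who "develops an adverse event grade 3 or higher that is possibly related to study treatment or wants to discontinue treatment". The consequence is stopping treatment.

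Section 8c sets the collection window for serious adverse events, which runs past early exit "until 30 days after a participant withdraws from the study". No section states a window for non-serious events after removal or discontinuation. None mentions person-time, an exposure-adjusted rate or time to first event.

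**The concern.** A count of events depends on how often events happen and on how long people are watched. Under Section 4f the watching can stop because of a safety event, so observation time may be shortest in the arm that tolerates its capsules worst. That arm's later events are then missing from its count. Serious events are partly protected by the 30-day window. Non-serious events are not, and Section 8a expects mainly gastrointestinal effects that could affect tolerability in this population.

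Safety and tolerability is the trial's main question. If exits are concentrated on TUDCA, the error in the count runs towards reassurance. Non-serious events that were never collected cannot be reliably recovered at the analysis stage, so the collection window has to be settled beforehand.

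**Working it through.** **Inputs from the documents.** Arm size 30 and planned drop-out 10% (Section 7c, sample size justification); follow-up 16 weeks (Section 4b). The plan's recruitment figure reproduces: 27 / (1 − 0.10) = 30 per arm. Planned drop-out is therefore 3 of 30.

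**Inputs not in the documents.** Adverse-event rates, exits by arm and exit times. These are assumed below and shown as ranges.

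**Step 1: loss of observation.** With k exits at week t, person-weeks = 30 × 16 − k × (16 − t). At a constant weekly rate, the count ratio equals the true rate ratio times (TUDCA person-weeks / placebo person-weeks). The inverse of that person-week ratio is the true rate ratio that would look like no difference. This step leaves out the events that trigger removal.

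| TUDCA exits | Placebo exits | Person-weeks | Ratio | True rate ratio hidden |
|---|---|---|---|---|
| 3 at week 8 | 0 | 456 vs 480 | 0.950 | 1.053 |
| 3 at week 4 | 0 | 444 vs 480 | 0.925 | 1.081 |
| 3 at week 2 | 0 | 438 vs 480 | 0.912 | 1.096 |
| 3 at week 4 | 1 at week 4 | 444 vs 468 | 0.949 | 1.054 |
| 6 at week 4 | 1 at week 4 | 408 vs 468 | 0.872 | 1.147 |
| 9 at week 4 | 2 at week 4 | 372 vs 456 | 0.816 | 1.226 |

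The first three rows put the whole planned 10% on TUDCA and none on placebo: a loss of about 5% to 9%. The 6 versus 1 row gives 1 − 0.872, about 13%. To hide a true ratio of 1.25 the person-week ratio must be 1 / 1.25 = 0.80, for example 40% of the TUDCA arm leaving at week 8 (384 / 480) with no placebo loss.

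**Step 2: put the triggering event back.** Suppose each exit in the 6 versus 1 case is caused by one recorded event, and every participant has b other events per 16 weeks, equally in both arms. Expected counts are 6 + 408b/16 on TUDCA and 1 + 468b/16 on placebo.

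| b | TUDCA count | Placebo count | Count ratio | Ratio per person-week |
|---|---|---|---|---|
| 1 | 31.5 | 30.25 | 1.04 | 1.19 |
| 2 | 57 | 59.5 | 0.96 | 1.10 |
| 4 | 108 | 118 | 0.92 | 1.05 |

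Each extra week-4 exit adds one event and loses 12/16 of b, so it lowers the arm's total only when b exceeds 16/12 = 1.33. In every row the arms have the same rate of other events and TUDCA has five more triggering events. The person-week rate shows that excess; the raw count understates it, and for b of 2 or 4 reverses it.

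**Step 3: can the drop-out component be relied on to show the imbalance?** Section 7 names no test for it. If 30% versus 10% were compared at 30 per arm (two-sided 0.05, normal approximation), the null standard error is √(2 × 0.2 × 0.8 / 30) = 0.1033 and the alternative standard error is √((0.3 × 0.7 + 0.1 × 0.9) / 30) = 0.1000. Then z = (0.20 − 1.96 × 0.1033) / 0.1000 = −0.02, which is power of about 49%.

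**The case against.** A reader might infer that an arm with more removals must record fewer events, or that TUDCA could pass as being as safe as placebo, or safer, on the primary outcome. The documents support neither.

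- Drop-out rate is the other half of the same outcome, and Section 7c also reports non-completion due to adverse events. With 6 versus 1 exits, 20% against 3% would stand beside the counts. This safeguard is real but partial: it does not repair the count, the plan has no rule for reading the two together, and drop-out is defined in two ways.
- The event that triggers removal is counted. With one other event per participant, TUDCA shows 31.5 against 30.25, which is more and not fewer. This stands.
- Six or nine exits are two or three times the planned three per arm. Section 3 reports that a 34-patient, 54-week ALS trial of the same dose found TUDCA well tolerated, with mild diarrhoea in two patients. The high gastrointestinal attrition cited there was with a different bile acid, UDCA. The larger scenarios are therefore illustrations and not forecasts.
- The incidence rate in Section 7c may already be meant as exposure-based. It is undefined, so this cannot be credited.
- Section 7d speaks of stopping treatment, so observation might continue. Section 4f says removal from the study, and the triggers only partly overlap. The documents leave the matter open.
- No test of event counts is named, so the comparison is descriptive as written. It remains half of the primary outcome.

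**Conclusion.** The concern holds in a limited form. Followed as written, the adverse-event count is biased towards whichever arm is observed for less time, and the bias falls mainly on later, non-serious events. Drop-out results would partly reveal the imbalance without correcting the count.

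The size rests on assumptions about exits and on a constant event rate. It is about 5–9% of the TUDCA count if all of the planned 10% drop-out falls on TUDCA between weeks 8 and 2, and about 13% of non-triggering events with 6 versus 1 exits at week 4. Whether the total count falls depends on how frequent other events are; in the 6 versus 1 case the threshold is 1.33 per participant over 16 weeks. At the planned drop-out the distortion is small. The change is worth making because it is cheap and because uncollected events cannot be restored later.

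**What to change.** 1. In Sections 7a and 7c, define one between-arm adverse-event measure: events per person-week of observation, with person-weeks shown by arm and a confidence interval. Beside it give the number of participants with at least one event, noting that early exit shortens this measure too.
2. State that this measure is read together with the drop-out rate, and use one definition of drop-out in both sections.
3. Reconcile Sections 4f and 7d on whether a participant who stops treatment leaves the study. Until that is settled the observation period is undefined.
4. State that adverse events, serious or not, are recorded to week 16 by phone or video in every randomised participant who stops capsules and does not refuse contact. Record last-dose and last-contact dates, so that events on and off capsules can be shown separately.

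Cost: wording in the outcome and analysis sections, two dates on the case report form, and a few extra contacts. The person-week rate assumes a roughly constant event rate. If events cluster in the first weeks, early exits lose fewer events than the lost time suggests and the rate over-corrects. Recording to week 16 reduces that dependence by keeping observation nearly equal between arms.
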